6.4.1.3. Combined Solicited and Unsolicited Adverse Events

Solicited AEs continuing beyond 7 days will be recorded by the sites and flagged using rules given in Section 5.2. They will be coded by MedDRA and following summary by decreasing frequency of SOC and preferred term within SOC will be provided:

- Solicited TEAEs continuing beyond 7 days
- Combined solicited TEAEs continuing beyond 7 days and unsolicited TEAEs

Following by-subject Listings will be provided:

- All solicited TEAEs continuing beyond 7 days

6.4.2. Laboratory Data

Not Applicable.

6.4.3. Vital Signs and Physical Examinations

The actual value and change from before study vaccine administration to after study vaccine administration will be summarized for each vital sign parameter: Systolic Blood Pressure, Diastolic Blood Pressure, Oral Temperature, Respiratory Rate and Heart Rate. In case of multiple measurements on Day 1 before vaccination, the closest measure from the time of vaccination will be used. In case of multiple measurements on Day 1 after vaccination, the closest measure from the time of vaccination will be used. Vital sign measurements will be presented in by-subject data listings.

Physical examination results at Baseline will be summarized. All physical examination findings will be presented in by-subject data listing.

6.5. Immunogenicity Evaluations

All Immunogenicity summaries to be produced by treatment group, for the Immunogenicity Evaluable Population and the Exposed Population.

6.5.1. GMT/GMC, GMR and GMFR

To estimate the immunogenicity response 1 month first vaccination, OPA titers (log₁₀) and IgG concentrations (mcg/mL) measured at Day 29 visit will be logarithmically transformed for analysis and GMTs/GMCs will be computed with 95% CI for each assay using ANOVA and ANCOVA.

- First model in an ANOVA with log₁₀-transformed concentrations/titers at Day 29 as the dependent variable and treatment group and study site as the fixed effects in the model.
- Second model in an ANCOVA with log₁₀-transformed concentrations/titers at Day 29 as the dependent variable, treatment group and study site as the fixed effects and log₁₀ baseline concentration/titer as the covariate.

The least squares means, and their 95% CIs calculated based on the ANOVA and ANCOVA will be back transformed and reported as the group GMT and GMC values. Comparisons between relevant groups will be based on the estimated adjusted GMTs measured at Day 29 visit for 24 serotypes in VAX-24 (of those 20 in PCV20), and mean square error calculated from the basic ANOVA model using contrast statements. The main comparison of interest will be the three VAX-24 dose levels group versus the PCV20 (20 serotypes) group. However, the three VAX-24 dose groups will also be compared in a pairwise fashion on a serotype-by-serotype basis. No adjustment for multiplicity will be applied and missing data will not be imputed. GMRs will also be calculated from the ANCOVA and ANOVA models.

The analysis of GMFR at Day 29 relative to Day 1 will also be computed using similar models:

- First model in an ANOVA with log₁₀-transformed fold ratio at Day 29 as dependent variable and treatment group and study site as the fixed effects in the model.
- Second model in an ANCOVA with log₁₀-transformed fold ratio at Day 29 as dependent variable, treatment group and study site as the fixed effects and log₁₀ baseline concentration/titer as the covariate.

The least squares means, and their 95% CIs calculated based on the ANOVA and ANCOVA will be back transformed and reported as the group GMFR value.

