5.6.2 Immune Response Assessments

Serum antibody responses to pneumococcal polysaccharides induced by vaccination will be measured using 2 standard assays, OPA and multiplexed Meso Scale Discovery (MSD) IgG.

The OPA assay has been developed and qualified by Nexelis, a GCP-compliant central laboratory, to analyze the 24 polysaccharide antigens contained in VAX-24. The OPA assay has been consistently used as the method for measuring the functional capacity of pneumococcal antibodies, as antibodies to pneumococcal PS protect the host by opsonizing pneumococci (marking pneumococci for destruction) for phagocytosis ([Burton and Nahm 2012](#)).

The MSD assay has been developed and qualified by Nexelis to measure IgG responses against the 24 polysaccharide antigens contained in VAX-24. The MSD multiplex electrochemiluminescent assay is an immunoassay platform that allows simultaneous measurement of responses against multiple antigens and has been used to evaluate responses to various pneumococcal conjugate vaccines ([Marchese 2009](#), [Goldblatt 2011](#), [Feysaguet 2019](#), and [Nolan 2020](#)).

The immune responses (as assessed by OPA and IgG assays) against the 20 polysaccharide antigens common to PCV20 and VAX-24 (1, 3, 4, 5, 6A, 6B, 7F, 8, 9V, 10A, 11A, 12F, 14, 15B, 18C, 19A, 19F, 22F, 23F and 33F) will be compared in the various treatment groups (VAX-24 at 3 different dose levels, and the comparator vaccine), and the 4 incremental polysaccharide antigens contained in VAX-24 (2, 9N, 17F and 20B) will be evaluated separately.

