2.2. Sample Size and Power

The sample size is not driven by statistical assumptions for formal hypothesis testing but was based on the safety objective for the study. A total of 200 subjects should provide sufficient information to assess safety and immunogenicity.

The sample size will also be adequate to establish variance of immune response in this target population and plan future studies.

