6.5.2. Threshold analyses

For the 4 non-PCV20 serotypes that are included in VAX-24 (i.e., 2, 9N, 17F and 20B), the adjusted proportion of subjects with a 4-fold increase in OPA titer will be evaluated using the following model:

- Logistic regression, with an indicator variable for achieving a 4-fold increase in OPA titer at Day 29 as the dependent variable, and treatment group and study site as fixed effects and log₁₀ baseline titer as a covariate. Proportion in each treatment group will be presented along their 95%CI. The difference of proportions in each of the three VAX-

24 dose levels group versus the PCV20 will also be presented along the 95% CI. If the lower bound of the 95% CI is >0.1 , the VAX-24 dose will be deemed statistically superior to PCV20.

Following summaries will also be provided for all serotypes:

- OPA titers:
 - Percentages of subjects achieving a 4-fold increase at Day 29 and associated Wilson score 95% CI and difference of proportions between pair-wise treatment groups using Fisher's exact test.
 - Percentages of subjects with titer \geq LLOQ at Day 29 and associated Wilson score 95% CI and difference of proportions between pair-wise treatment groups using Fisher's exact test.
- IgG concentrations:
 - Percentages of subjects achieving a 4-fold increase at Day 29 and associated Wilson score 95% CI and difference of proportions between pair-wise treatment groups using Fisher's exact test.
 - Percentages of subjects with titer \geq LLOQ at Day 29 and associated Wilson score 95% CI and difference of proportions between pair-wise treatment groups using Fisher's exact test.

Following Figures will be provided on the IEP:

- A reverse cumulative distribution curve of OPA titers on Day 1 and Day 29 by treatment groups for each serotype
- A reverse cumulative distribution curve of IgG concentrations on Day 1 and Day 29 by treatment groups for each serotype
- Bar Plot of OPA GMTs at Day 29 from ANOVA model by treatment group and serotype
- Bar Plot of IgG GMCs at Day 29 from ANOVA model by treatment group and serotype
- Bar Plot of percentages of subjects achieving a 4-fold increase in OPA titers by serotype
- Bar Plot of percentages of subjects achieving a 4-fold increase in IgG concentrations by serotype
- Forest Plot of OPA GMRs and GMFRs from ANOVA model at Day 29 for VAX-24 compared with PCV20 by serotype
- Forest Plot of IgG GMRs and GMFRs from ANOVA model at Day 29 for VAX-24 compared with PCV20 by serotype

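### For serotypes 2, 9N, 17F and 20B, which PCV20 does not contain, one pooled four-arm residual variance gives intervals that are too narrow or too wide unless the PCV20 and VAX-24 SDs happen to be equal

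*SAP*

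**What the plan says.** SAP 6.5.1 models log10 Day 29 OPA titers and IgG concentrations by ANOVA with "treatment group and study site as the fixed effects in the model". A second model, an ANCOVA, adds the log10 baseline value. Comparisons use adjusted GMTs "measured at Day 29 visit for 24 serotypes in VAX-24 (of those 20 in PCV20"), with the "mean square error calculated from the basic ANOVA model using contrast statements". Protocol 9.6.1 says the same. Models of the same form are fitted to the log10 fold ratio for GMFR.

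Two sets of comparisons follow. "The main comparison of interest will be the three VAX-24 dose levels group versus the PCV20 (20 serotypes) group", and "the three VAX-24 dose groups will also be compared in a pairwise fashion on a serotype-by-serotype basis".

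Protocol 5.6.2 states that "the 4 incremental polysaccharide antigens contained in VAX-24 (2, 9N, 17F and 20B) will be evaluated separately". The only separate analysis described is the logistic model for a 4-fold OPA rise (Protocol 9.6.2), which SAP 6.5.2 introduces with "For the 4 non-PCV20 serotypes that are included in VAX-24 (i.e., 2, 9N, 17F and 20B"). The forest plots of GMRs and GMFRs against PCV20 in SAP 6.5.2 are by serotype and are not restricted to the 20 shared ones.

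Neither document provides arm-specific variances, a variance check, a sensitivity model, or dose contrasts that leave out the PCV20 arm. SAP 2.2 calls the sample size "adequate to establish variance of immune response in this target population and plan future studies".

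**The concern.** For 20 serotypes all four arms are vaccinated, and a common residual variance is an ordinary working assumption. For serotypes 2, 9N, 17F and 20B the PCV20 arm is in effect unvaccinated: its Day 29 values reflect background antibody and assay variation, whereas the VAX-24 arms also carry between-subject variation in response to vaccine. Nothing in the documents supports equal SDs there.

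The case is clearest for GMFR. SAP 5.2 sets values below the LLOQ to the LLOQ itself when fold ratios are calculated. A PCV20 subject below the LLOQ at both visits therefore has a fold ratio of exactly 1, that is 0 on the log10 scale, with no spread. A smaller PCV20 SD is the natural expectation. For Day 29 GMT/GMC the direction cannot be foreseen.

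At stake are the error bars for the four serotypes that distinguish VAX-24 from PCV20. They include the comparisons between VAX-24 doses in a trial titled dose-finding, where an arm with no antigen would set part of the error term.

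**Working it through.** The plan states no SD, mean square error or interval width, so there is no figure of that kind to reproduce. Its allocation is consistent: 200/4 = 50 per arm.

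**Inputs from the documents.** 50 per arm (SAP 2.3); about 20 sites (Protocol synopsis), fitted as fixed effects; two-sided 0.05 (SAP 6.1.1).

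**Assumptions.** All 50 per arm evaluable; the same SD, s, in the three VAX-24 arms; r = PCV20 SD / VAX-24 SD between 0.5 and 1.5.

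**Formulas.** With equal arms the pooled mean square error estimates s²(3 + r²)/4. The planned half-width divided by the correct one is then:

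- dose versus dose, and each VAX-24 GMT: √((3 + r²)/4)
- VAX-24 versus PCV20: √((3 + r²)/(2(1 + r²)))
- PCV20 GMT: √((3 + r²)/4)/r

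At r = 0.5 these are √(3.25/4) = 0.90, √(3.25/2.5) = 1.14 and 0.90/0.5 = 1.80. At r = 1.5 they are √(5.25/4) = 1.15, √(5.25/6.5) = 0.90 and 1.146/1.5 = 0.76.

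**Results** (width ratio, with approximate coverage of a nominal 95% interval):

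| r | Dose vs dose | VAX-24 vs PCV20 | PCV20 GMT |
|---|---|---|---|
| 0.5 | 0.90 (92.3%) | 1.14 (97.5%) | 1.80 (about 100%) |
| 0.8 | 0.95 (93.8%) | 1.05 (96.1%) | 1.19 (98.1%) |
| 1.0 | 1.00 (95.0%) | 1.00 (95.0%) | 1.00 (95.0%) |
| 1.25 | 1.07 (96.4%) | 0.94 (93.6%) | 0.85 (90.6%) |
| 1.5 | 1.15 (97.5%) | 0.90 (92.2%) | 0.76 (86.6%) |

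The dose-versus-dose error rate is thus about 7.5% to 7.7% at r = 0.5 and 2.4% to 2.5% at r = 1.5; the last digit depends on whether a normal or t reference is used. The dose-versus-dose and VAX-24-versus-PCV20 errors always go in opposite directions.

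**Simulation check.** 4,000 runs per value of r, with 20 sites as fixed effects, gave dose-versus-dose coverage of 92.3% at r = 0.5 and 97.5% at r = 1.5. For VAX-24 versus PCV20 it gave 97.2% and 92.7%. The PCV20 GMT interval covered 99.9% and 88.6%.

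**With a VAX-24-only error term.** Simulated dose-versus-dose coverage was 94.5% to 95.1% at every r tried. Residual df fall from 200 − 4 − 19 = 177 to 150 − 3 − 19 = 128, and the t quantile moves from 1.973 to 1.979.

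**On the fold scale**, for illustration only, with an assumed s = 0.6 log10 and r = 0.5:

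- Dose versus dose, planned: 10^(1.973 × 0.6 × 0.901 × √(2/50)), or ×/÷ 1.63. VAX-24-only: 10^(1.979 × 0.6 × √(2/50)), or ×/÷ 1.73.
- VAX-24 versus PCV20, planned: ×/÷ 1.63. Unequal variances: 10^(1.98 × 0.6 × √(1.25/50)), or ×/÷ 1.54.

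**The case against.** The best defence is that pooling is the standard ANOVA assumption and is exact when the SDs are equal. The documents give no SD, so no error has been shown to exist, and across the assumed range its sign reverses. Moderate inequality does little harm. The analyses are secondary and unadjusted for multiplicity, and no dose-selection rule rests on these contrasts. The main comparison with PCV20 is confined to the 20 shared serotypes, and the one decision rule for the other four is the logistic 4-fold-rise analysis, which does not use this mean square error. Reverse cumulative curves by arm would also show a difference in spread.

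All of this stands and limits the weight of the point. It does not supply a reason to expect equal variances where one arm gets no antigen.

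Two stronger readings are tempting and are not supported:

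- A reader might infer that the pooled mean square error is the variance the sponsor will carry into future planning. SAP 2.2 says only that the sample can establish variance; it names no estimator. SAP 6.1.1 already plans SDs for continuous variables and SAP 6.5 presents summaries by treatment group, though neither specifies the log10 scale.
- A reader might infer that the common baseline slope invalidates the ANCOVA. That model is secondary, and under randomisation a common slope still gives a consistent estimate of the average difference between arms.

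**Conclusion.** The point holds as a conditional one. For serotypes 2, 9N, 17F and 20B the planned intervals have the right width only if the PCV20 and VAX-24 SDs agree, and the plan has no provision for the case where they do not. It would go too far to say that the intervals are wrong: that cannot be established without SDs, and for Day 29 GMT/GMC even the direction is unknown. For GMFR the PCV20 SD is expected to be smaller. Dose-versus-dose intervals would then be too narrow, and PCV20 and VAX-24-versus-PCV20 intervals too wide.

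The size depends on the assumed ratio. Between 0.8 and 1.25 the dose-versus-dose and VAX-24-versus-PCV20 widths are off by at most about 7%; at 0.5 or 1.5 they are off by 10% to 15%, and the PCV20 interval by more. Only error bars are in question: pooling the variance does not bias the GMTs or GMRs. This is a modest, inexpensive improvement.

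**What to change.** In SAP 6.5.1, for serotypes 2, 9N, 17F and 20B, fit the planned ANOVA and ANCOVA, for both Day 29 values and fold ratios, with arm-specific residual variances (for example PROC MIXED with REPEATED / GROUP=treatment and Satterthwaite or Kenward-Roger degrees of freedom). The narrower alternative is a VAX-24-only error term for the dose-versus-dose contrasts; that leaves the PCV20 intervals and the comparisons with PCV20 as they are. In either case, report the log10 SD by arm and serotype and state that the VAX-24 SDs are the ones used to plan later studies. A treatment-by-baseline term in the secondary ANCOVA is optional.

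The cost is a sentence or two in the SAP, one program option, and the small loss of residual degrees of freedom shown above.

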6.5.2. Threshold analyses

For the 4 non-PCV20 serotypes that are included in VAX-24 (i.e., 2, 9N, 17F and 20B), the adjusted proportion of subjects with a 4-fold increase in OPA titer will be evaluated using the following model:

- Logistic regression, with an indicator variable for achieving a 4-fold increase in OPA titer at Day 29 as the dependent variable, and treatment group and study site as fixed effects and log₁₀ baseline titer as a covariate. Proportion in each treatment group will be presented along their 95%CI. The difference of proportions in each of the three VAX-

24 dose levels group versus the PCV20 will also be presented along the 95% CI. If the lower bound of the 95% CI is >0.1 , the VAX-24 dose will be deemed statistically superior to PCV20.

Following summaries will also be provided for all serotypes:

- OPA titers:
 - Percentages of subjects achieving a 4-fold increase at Day 29 and associated Wilson score 95% CI and difference of proportions between pair-wise treatment groups using Fisher's exact test.
 - Percentages of subjects with titer \geq LLOQ at Day 29 and associated Wilson score 95% CI and difference of proportions between pair-wise treatment groups using Fisher's exact test.
- IgG concentrations:
 - Percentages of subjects achieving a 4-fold increase at Day 29 and associated Wilson score 95% CI and difference of proportions between pair-wise treatment groups using Fisher's exact test.
 - Percentages of subjects with titer \geq LLOQ at Day 29 and associated Wilson score 95% CI and difference of proportions between pair-wise treatment groups using Fisher's exact test.

Following Figures will be provided on the IEP:

- A reverse cumulative distribution curve of OPA titers on Day 1 and Day 29 by treatment groups for each serotype
- A reverse cumulative distribution curve of IgG concentrations on Day 1 and Day 29 by treatment groups for each serotype
- Bar Plot of OPA GMTs at Day 29 from ANOVA model by treatment group and serotype
- Bar Plot of IgG GMCs at Day 29 from ANOVA model by treatment group and serotype
- Bar Plot of percentages of subjects achieving a 4-fold increase in OPA titers by serotype
- Bar Plot of percentages of subjects achieving a 4-fold increase in IgG concentrations by serotype
- Forest Plot of OPA GMRs and GMFRs from ANOVA model at Day 29 for VAX-24 compared with PCV20 by serotype
- Forest Plot of IgG GMRs and GMFRs from ANOVA model at Day 29 for VAX-24 compared with PCV20 by serotype

Finally, all immunogenicity data will be provided by-subject data listings on the Exposed Population.

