9.6 Immunogenicity Analysis

9.6.1 GMT/GMR

Immunogenicity analyses will be performed for both OPA (titers) and IgG (mcg/mL). All immunogenicity analyses will be based on the IEP and Exposed Population.

The GMTs and GMCs will be analyzed via linear models. The primary model is an analysis of variance (ANOVA), with logarithmically transformed titers (\log_{10}) as the dependent variable and treatment group and study site as the fixed effects in the model. The results included in the main tables of this report will be based on this basic ANOVA model. As a secondary analysis, to remove the effect of baseline concentration on the GMTs, an analysis of covariance (ANCOVA) will also be performed. The ANCOVA includes treatment group and study site as the fixed effects and \log_{10} baseline titer as the covariate in the model. The rationale for including baseline values as a covariate is that prior data have shown vaccine response is correlated with baseline antibody levels.

The least squares means and their 95% confidence intervals (CIs) calculated based on the ANOVA and ANCOVA will be back transformed and reported as the group GMT and GMC values (adjusted for the mean baseline in the case of the ANCOVA). GMRs will also be calculated from the ANCOVA and ANOVA models.

Comparisons between relevant groups will be based on the estimated adjusted GMTs measured at Day 29 for 24 serotypes in VAX-24 (of those 20 in PCV20), and mean square error calculated from the basic ANOVA model using contrast statements. The analysis of GMFR relative to Day 1 will also be computed using similar models.

The main comparison of interest will be the three VAX-24 dose levels group versus the PCV20 (20 serotypes) group. However, the three VAX-24 dose groups will also be compared in a pairwise fashion on a serotype-by-serotype basis. No adjustment for multiplicity will be applied and missing data will not be imputed.

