6.1.3. Adjustments for Covariates

The randomization in this study will not be stratified.

The following variables will be used for adjustment in immunogenicity analyses:

- For the Analysis of variance (ANOVA), study site will be included as fixed effect in the model.
- For the Analysis of covariance (ANCOVA) and the logistic regression, study site will be included as fixed effect and the log baseline titer will be included as covariate in the model. In case the model does not converge, the log₁₀ baseline titer will be removed from the model and a footnote explicating the change will be added.

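### SAP 6.5.2 uses the Day 1 titer in the 4-fold-rise comparison only for OPA on the four serotypes absent from PCV20; the 20 shared serotypes and all IgG get a Fisher test with no CI for the difference

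*SAP*

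**What the plan says.** SAP 6.5.2 treats the 4-fold rise in two ways.

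- **Adjusted.** "For the 4 non-PCV20 serotypes that are included in VAX-24 (i.e., 2, 9N, 17F and 20B), the adjusted proportion of subjects" with a 4-fold OPA rise comes from a model: "Logistic regression, with an indicator variable for achieving a 4-fold increase in OPA titer at Day 29 as the dependent variable", with treatment, site and log10 baseline titer as predictors. SAP 6.1.3 confirms that "study site will be included as fixed effect and the log baseline titer will be included as covariate in the model". Each dose-versus-PCV20 difference gets a 95% CI, and a superiority rule (lower bound above 0.1) applies.
- **Unadjusted.** "Following summaries will also be provided for all serotypes": for OPA and again for IgG, "Percentages of subjects achieving a 4-fold increase at Day 29 and associated Wilson score 95% CI and difference of proportions between pair-wise treatment groups" by Fisher's exact test. As worded, the Wilson interval belongs to each arm's percentage; none is named for the difference. Protocol 9.6.2 has the same split and makes the Fisher tests optional.

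The sentence "The main comparison of interest will be the three VAX-24 dose levels group versus the PCV20 (20 serotypes) group" is in SAP 6.5.1, which covers GMTs, GMCs, GMRs and GMFRs. That section has an ANCOVA with log10 baseline as its second model, both for Day 29 values and for the log10 fold ratio.

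**The concern.** Protocol 9.6.1 justifies adjusting GMTs on the ground that "prior data have shown vaccine response is correlated with baseline antibody levels". A 4-fold rise has the Day 1 value in its definition (SAP 5.2, fold ratio), so the argument carries over. Day 1 serum is drawn from every subject and the IEP requires a baseline result, so no new data are needed.

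Yet adjustment is confined to four serotypes that PCV20 does not contain, where one would expect the arms to differ most and precision to matter least. For the shared serotypes, where smaller differences between doses and PCV20 are of interest, the reader gets a p-value without an interval. Neither document explains the restriction.

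At stake is how precisely a dose-finding trial describes responder differences, and how far those differences carry chance Day 1 imbalance, since randomisation is unstratified (SAP 2.3).

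**Working it through.** **Inputs from the documents.** 200 subjects at 1:1:1:1, so 200/4 = 50 per arm, as SAP 2.3 states. Two-sided 0.05 (SAP 6.1.1). About 20 sites (Protocol synopsis), so 200/20 = 10 subjects per site. SAP 2.2 says the sample size does not rest on hypothesis-testing assumptions, so there is no stated power to reproduce. No responder rate, SD or correlation is given; all of those below are assumptions.

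**1. Unadjusted precision at 50% vs 75%.** Var = p1(1-p1)/n + p2(1-p2)/n = 0.25/50 + 0.1875/50 = 0.00875. SE = 0.0935; 95% half-width = 1.96 × 0.0935 = 0.183.

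**2. What drives the gain.** Let ρ be the Day 1-Day 29 correlation of log10 titers and k the Day 29 SD divided by the Day 1 SD. The correlation of Day 1 with the log fold rise is (ρk - 1)/√(1 + k² - 2ρk). It vanishes when ρk, the slope of Day 29 on Day 1, equals 1. A stronger Day 1-Day 29 correlation can therefore mean less gain.

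**3. Simulation, two arms of 50.** Bivariate normal log10 titers; unadjusted Wald difference against the standardised difference from a logistic model with treatment and baseline only.

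| ρ | k | Corr. of Day 1 with log rise | Power, unadjusted to adjusted |
|---|---|---|---|
| 0.3 | 1 | -0.7/√1.4 = -0.59 | 74.4% to 84.2% |
| 0.5 | 1 | -0.5/1 = -0.50 | 74.5% to 80.8% |
| 0.7 | 1 | -0.3/√0.6 = -0.39 | 73.9% to 77.8% |
| 0.5 | 1.33 | -0.335/√1.439 = -0.28 | 74.1% to 75.8% |

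The variance ratio (adjusted/unadjusted) was 0.87 in the second row. At ρ = 0.7, k = 1.33 the slope is 0.93 and the ratio was 1.01. With k = 0.8 the power gain reached 12 points. Over all such cases the ratio ran from 0.77 to 1.01. At 0.77 the half-width falls from 0.183 to 0.183 × √0.77 = 0.161. Type I error was 5.3-5.6% adjusted and 5.3-5.9% unadjusted.

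**4. The SAP's LLOQ rule.** SAP 5.2 sets values below LLOQ to LLOQ for fold ratios and to half of it for titers. With 25% of Day 1 values below LLOQ the ratio was 0.86-1.01; with 50% below, 0.96-1.00.

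**5. Fisher's own share.** Exact enumeration at 50 per arm, 50% vs 75%: Fisher 67.5%, pooled z 74.5%. Those 7 points are Fisher's conservatism (actual type I error 2.8-3.5% at common rates of 0.5 to 0.8), not missing adjustment.

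**6. Site terms.** A separate four-arm simulation, 60% vs 80%, 20 sites with no true site effect:

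| Corr. of Day 1 with latent rise | Variance change, baseline only | Baseline plus site |
|---|---|---|
| 0 | about 0% | +10% |
| -0.3 | -4% | +8% |
| -0.5 | -17% | -5% |
| -0.7 | -27% | -15% |

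With site in the model, some site coefficients separated or failed to converge in 82-85% of runs (32-34% at 60% vs 60%). Type I error at 60% vs 60% was 6.7-7.7%, against 4.9-5.6% with baseline only. The -0.7 row is extreme: with equal SDs the step 2 formula reduces to -√((1-ρ)/2), so -0.7 needs ρ = 1 - 2 × 0.49 = 0.02.

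**7. Chance imbalance.** One standard error of Day 1 imbalance is √(2/50) = 0.2 SD. It moved the raw difference by 2-4 percentage points and the adjusted difference by about 0.

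**The case against.** The strongest reply is that little is lost. The GMFR ANCOVA in SAP 6.5.1 already adjusts the log fold ratio for baseline in both assays, and a responder is that same ratio cut at 4. The listed secondary endpoints (SAP 3.3) are GMTs and GMCs; part of that section is redacted, but in the visible text the shared-serotype responder rate carries no decision rule. The logistic model is attached to the one superiority rule shown in the immunogenicity plan, which could explain more elaborate modelling there. The Protocol's remark on baseline is qualitative and was made about GMTs. Nor is the remedy just the existing model run on more serotypes, because it drops the site effect.

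Most of this stands and sets the weight of the point. It does not explain why a responder difference should have an adjusted estimate and a CI for four serotypes and neither for the other twenty. The site objection concerns the SAP's full model; with baseline only, no case showed a material loss.

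A reader might infer that the plan's principal comparison goes unadjusted. It does not: that wording belongs to the GMT/GMC analysis, which has an ANCOVA, though as the second model.

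**Conclusion.** The asymmetry is real and neither document explains it. It is a matter of efficiency and consistency in a supportive analysis.

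At 50 per arm and 50% vs 75%, baseline-only standardisation changes the variance of the difference by about 0 to -23%, or about 0 to 12 power points over an unadjusted Wald test. The gain shrinks to little or nothing when many Day 1 values are below LLOQ or when the slope of Day 29 on Day 1 is near 1. Every rate, SD, correlation and LLOQ share here is assumed, and the true values will differ by serotype.

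Two further inferences are not supported. The Fisher comparison is not biased or invalid: randomisation protects it, and chance imbalance affects only the single realised trial. Nor is a loss of precision certain, since the documents give no correlation from which to establish it. The missing CI for the difference does not depend on any of these assumptions.

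**What to change.** In SAP 6.5.2 add, as a supportive analysis for all 24 serotypes and both assays, the standardised (marginal) difference in 4-fold-rise proportions with its 95% CI, for each VAX-24 dose versus PCV20 and for each pair of doses. Take it from a logistic model with treatment and log10 Day 1 value. Leave out the roughly 20 site terms and say why. This also avoids the fallback in SAP 6.1.3, which on non-convergence removes baseline and keeps site. Keep the raw percentages with Wilson intervals. Where the model cannot be fitted, for instance with rates near 0% or 100%, report the raw difference with a CI. Settle the wording before unblinding.

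The cost is SAP text and more model runs, with no new data. The new model will differ from the existing site-adjusted one for serotypes 2, 9N, 17F and 20B, so the SAP should state which of the two carries the superiority rule. If the sponsor prefers not to add it, the SAP should say why adjustment stops at four serotypes and should still give a CI for the raw differences.
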